## **2.6 Safety analyses**

The assessment of safety was based mainly on the frequency of adverse events and on the number of laboratory values that fall outside of pre-determined ranges. Other safety data were considered as appropriate.

### **2.6.1 Adverse events (AEs)**

Treatment emergent events are defined as all adverse events started at baseline or later.

Treatment emergent adverse events were summarized by presenting, for each treatment group, the number and percentage of patients having any adverse event, having an adverse event in

each body system and having each individual adverse event. Any other information collected (e.g. severity or relatedness to study medication) were listed as appropriate.

Data collected by AE CRFs and by Infection CRFs were coded using MedDRA. The number of AE/patients with AE was summarized by MedDRA system organ class and preferred term. Additionally, AE will be summarized

- by maximum severity,
- for AE with suspected drug relation,
- for serious AE (SAE), and
- for AE leading to permanent discontinuation of study drug.

In addition to being analyzed together with AE data, the incidence of bacterial, viral and fungal infections will be tabulated separately for all infections

- by maximum severity,
- for infections with suspected drug relation,
- for serious infections and
- for infections leading to premature discontinuation of study drug.

Infections were defined as adverse events as adverse events in primary system organ class “Infections and infestations”.

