### **End of Treatment/End of Study – Visit 9a and Visit 9 (Month 12)**

In case of early discontinuation of study drug treatment, Month 12 assessments need to be performed

- as soon as possible after study drug discontinuation (Visit 9a).
- additionally at the originally planned time point, i.e. 12 months post randomization (Visit 9). At Month 12 for patients who discontinued study drug prematurely, only the following numbers 1, 2, 4, 5, 6, 8, 9, and 13 are mandatory.

1. A complete physical examination will be performed.
2. Vital signs will be measured.
3. Returned study medication (everolimus) and returned tacrolimus will be counted.
4. Venous blood will be drawn for measurement of hematology and biochemistry.
5. Venous blood will be drawn for CMV monitoring (including pp65 Ag).
6. Venous blood will be drawn for HCV monitoring: Viral load (RNA level), in HCV positive patients only.
7. Venous blood will be drawn for measurement of the tacrolimus and everolimus C0-h blood levels.
8. Urinalysis will be performed.
9. GFR will be calculated.
10. A control biopsy will be performed for analysis of allograft fibrosis (only HCV positive patients).

11. End of Study / End of Treatment information will be obtained.
12. Menopausal status will be recorded and in all women of childbearing potential a pregnancy test will be performed ( $\beta$ -HCG) (see also section 7.3).

For patients who prematurely discontinued study drug, information about rejection episodes, biopsies, opportunistic infections, malignancies and the current immunosuppression will be collected. SAEs will be collected until 30 days after the patient has stopped study participation (or longer in case of suspected relationship).

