#### **Adverse events/infections**

Data collected by AE CRFs and by Infection CRFs will be coded using MedDRA. The number of AE/patients with AE will be summarized by MedDRA system organ class and preferred term. Additionally, AE will be summarized by maximum severity, and for AE with suspected drug relation, serious AE (SAE), and AE leading to permanent discontinuation of study drug. In addition to being analyzed together with AE data, the incidence of bacterial, viral and fungal infections will be tabulated separately for all infections, by maximum severity, for infections with suspected drug relation, serious infections and infections leading to premature discontinuation of study drug. These summary tables will include adverse events of special interest, such as New Onset of Diabetes Mellitus (NODM, for definition see [Section 7.6.4](#)), *de novo* HCC malignancies, HCV- and HCC-related fibrosis.

All information pertaining to AE noted during the study will be listed by treatment group and patient, detailing the verbatim term given by the investigator, MedDRA preferred term and system organ class, start/end dates, severity, seriousness, relationship to study drug and action taken. The AE onset will also be shown relative (in number of days) to the date of initial dose.

AE starting before, or 28 or more days after the discontinuation of study medication, will not be considered as treatment-emergent and will not be included in AE/infection summary tables but listed only.

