### **2.6.3 Laboratory data**

Abnormalities according notable criteria (see Appendix 2 of the study protocol) were identified. The proportions of patients with clinically notable abnormalities according to the notable criteria were summarized. Descriptive statistics of absolute values as well as change from baseline of all laboratory variables were presented by visit and treatment group. A by-

patient listing of all clinically notable abnormal laboratory data was generated. Only assessments obtained up to 28 days after the discontinuation of study medication will be considered “on-treatment” and analyzed with relationship to immunosuppressive therapy.

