**Changes in statistical methods in comparison to the protocol:**

The Virus (HCV, CMV) and Hepatocellular Carcinoma (HCC) related secondary objective “• To evaluate rates of progression of HCV related allograft fibrosis are deleted. Reason is, that the in case from HCV the biopsies were not performed adequately.

The incidence of proteinuria of  $0.5 - <1.0$  g/day,  $1.0 - <3.0$  g/day and  $\geq 3.0$  g/day could not be analysed, because in urine analysis protein is measured in g/l and not in g/day. Therefore, proteinuria could be only documented as adverse event. Therefore proteinuria is defined as further adverse event of special interest.

CNV viral infection were defined as further adverse event of special interest.

Treatment emergent events were defined as all adverse started at baseline or later.

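### The SAP drops the protocol's 28-day limit on treatment-emergent events without a reason, and the open window no longer matches what is clearly collected after study drug is stopped

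*SAP*

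**What the plan says.** **Window for adverse events.** Protocol 10.5.2 (Adverse events/infections) closes the window: "AE starting before, or 28 or more days after the discontinuation of study medication, will not be considered as treatment-emergent". Such events are listed but not tabulated. SAP 2.6.1 gives only a start: "Treatment emergent events are defined as all adverse events started at baseline or later". SAP 4, under the changes in statistical methods, repeats this ("Treatment emergent events were defined as all adverse started at baseline or later") and gives no reason. The fibrosis and proteinuria changes in the same list each carry one.

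**Window for laboratory data and vital signs.** SAP 2.6.3 keeps the limit: "Only assessments obtained up to 28 days after the discontinuation of study medication will be considered" on-treatment. SAP 2.6.4.2 does the same for vital signs.

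**Collection after drug stop.** Protocol section 7 (Visit 9a and Visit 9) says that for these patients "information about rejection episodes, biopsies, opportunistic infections, malignancies and the current immunosuppression will be collected", and that "SAEs will be collected until 30 days after the patient has stopped study participation". At their Month 12 visit, "only the following numbers 1, 2, 4, 5, 6, 8, 9, and 13 are mandatory", but the numbered list ends at 12.

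**Summary measure.** SAP 2.6.1 reports the number and percentage of patients with an event. SAP 5.1.1 counts duration of exposure to end of study, including time after end of treatment.

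**The concern.** SAP 2.6 rests safety mainly on AE frequency and on laboratory values outside set ranges. Those two pillars now use different windows. An event that starts months after the regimen was stopped is treatment-emergent in the AE table, while a laboratory value from the same day is not on-treatment.

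The open window also reaches into a period in which collection is clearly stated only for some categories. SAEs, malignancies and opportunistic infections are followed. Non-serious AEs and ordinary infections are not named. The main tables may therefore combine on-regimen events of every kind with off-regimen events of selected kinds. Two outcomes are exposed to this because the SAP identifies them from AE terms, which can be non-serious: proteinuria (SAP 2.5.2 and 4) and new-onset diabetes (SAP 5.5.2).

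The trial is open-label and one arm receives an added drug, so stopping could differ by arm. If off-drug capture is incomplete, crude percentages keep such patients in the denominator for a full year while part of their follow-up goes unrecorded.

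**Working it through.** The plan states no figure on this point, so none can be reproduced. The check compares the texts and then illustrates the possible size.

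**1. What the definition does by itself.** The protocol rule counts onsets up to day 27 after stopping. The SAP rule counts those and all later ones. For any set of recorded events, the SAP count is therefore equal to or higher than the protocol count.

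**2. What is collected off drug.** The texts point in two directions.

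- Narrow: the section 7 list quoted above; safety contact specified, as a minimum, for 30 days after the last dose (protocol 6.6.6 and 7); and no printed item among those mandatory at Month 12 that asks about AEs.
- Wide: protocol 7.6.1 has AEs sought at each study visit, with no exception for patients off drug; 7.6.1 (Infections) requires every infection episode to be recorded; the assessment schedule shows AEs and infections as necessary across visits, with a mark at a final visit; and 5.2 keeps patients who stop drug in the study.
- Undetermined: item 13. At Visit 2 and at Visits 3–8, the last numbered item covers rejections, infections and other (S)AEs, so item 13 may have been the matching item. It may also refer to the unnumbered paragraph after item 12. The text does not say.

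**3. Illustration if capture does end shortly after stopping.** All inputs are assumptions: the same true 12-month incidence p in both arms, a constant hazard r = −ln(1 − p)/12 per month, a share d who stop drug, and capture ending at month c for them. Observed percentage = (1 − d)·p + d·q, with q = 1 − exp(−c·r).

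Take 30% vs 15% stopping, all at month 3, with capture to month 4:

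- p = 20%: r = 0.0186 and q = 7.2%. Observed 0.70×20 + 0.30×7.2 = 16.2% vs 0.85×20 + 0.15×7.2 = 18.1%, ratio 0.89.
- p = 40%: r = 0.0426 and q = 15.7%. Observed 32.7% vs 36.3%, ratio 0.90.

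Other scenarios, with capture ending 30 days after stopping in a 360-day year, give these spurious differences in percentage points (arm with more stops minus the other):

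| True incidence | 30% vs 20%, stops uniform over the year | 40% vs 10%, uniform | 40% vs 10%, all at day 30 |
|---|---|---|---|
| 10% | −0.4 | −1.2 | −2.5 |
| 30% | −1.2 | −3.5 | −7.3 |
| 60% | −2.1 | −6.2 | −13.8 |
| 95% | −2.0 | −5.9 | −16.7 |

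Worked cell (30%, all at day 30): risk to day 60 is 1 − 0.7^(60/360) = 5.8%. Observed 0.6×30 + 0.4×5.8 = 20.3% vs 0.9×30 + 0.1×5.8 = 27.6%, a difference of −7.3. With equal stopping, every difference is 0.

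**4. Does the 28-day window alone remove the gap?** No. In the month-3 scenario with p = 20%, c becomes 3 + 28/30 = 3.93 months and q = 7.1%. The result is 16.1% vs 18.1%, ratio 0.89. With uniform stopping, 40% vs 10% and p = 30%, the gap is −3.6 points instead of −3.5.

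**5. Does on-treatment person-time remove it?** Under these assumptions, yes. Person-months to first event or end of window are [(1 − d)·p + d·q]/r. For p = 20% and c = 4 this gives 8.69 and 9.72 per patient. The rates are 0.1615/8.69 = 0.0186 and 0.1808/9.72 = 0.0186, equal in both arms.

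**The case against.** The strongest reply has four parts.

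- The change is openly declared in SAP 4. Counting events to end of study is a legitimate treatment-policy summary, and it matches the exposure definition in SAP 5.1.1.
- A reader might infer that the SAP definition itself pushes AE rates down in the arm with more stops. It cannot, because an open window only adds events relative to the protocol rule. Any low bias would come from incomplete collection combined with crude percentages, and the protocol's own tables share that weakness (step 4).
- A reader might also infer that non-serious events off drug were not collected. The documents do not establish this. Protocol 7.6.1 and the assessment schedule call for AEs without exempting these patients, the section 7 list does not say it is exhaustive, and item 13 is unresolved.
- SAP 2.6.1 also tabulates drug-related AEs and AEs leading to discontinuation, which limits misattribution of late events.

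The second and third parts stand in full and set the limits of this point. The first stands for categories followed throughout, such as SAEs. It does not justify a single open window for all AEs when capture of some is uncertain, nor does it explain why laboratory data and vital signs keep 28 days. The fourth reduces the problem for those subsets only. The overall AE and infection tables are unaffected by it.

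**Conclusion.** The point holds as a mismatch of windows and collection. The SAP removes the protocol's 28-day limit for AEs without a reason, keeps it for laboratory data and vital signs, and so tabulates a period for which capture of non-serious AEs and ordinary infections is uncertain. The main AE and infection tables may mix on-regimen events with selectively captured off-regimen events. Tables of SAEs and other followed categories gain off-drug events and can move in either direction.

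A low bias in the arm with more stops is conditional. It needs both incomplete off-drug capture and unequal drug discontinuation. The documents give no drug discontinuation by arm: SAP 2.3.6 says only that study discontinuations are below 20%, which is a different quantity and not split by arm. The actual size therefore cannot be computed. Under the assumed scenarios the gap is about 0.4 to 6 points with stopping spread over the year, up to about 17 points with early and very unequal stopping, and zero with equal stopping.

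**What to change.** 1. In SAP 2.6.1, base the main AE and infection tables on the protocol 10.5.2 window: onset from baseline and less than 28 days after study drug is stopped. State how day 28 itself is treated, because the laboratory and vital-sign rule includes it and the protocol AE rule does not.
2. Add exposure-adjusted rates or time to first event for the main AE and infection categories, since the window alone leaves the unequal-follow-up gap. Use on-treatment time, for example to the date of last treatment in SAP 2.1.1 plus the 28-day window, and not the end-of-study exposure of SAP 5.1.1. These methods still assume that stopping is unrelated to the risk of later events, and the report should say so.
3. Tabulate later events separately as post-treatment.
4. Show full-follow-up tables only for categories collected throughout: SAEs, deaths, malignancies and opportunistic infections.
5. State what was collected after drug stop. Reconcile the section 7 list and its item 13 with the assessment schedule and protocol 7.6.1, and give the reason for any departure from protocol 10.5.2 in SAP 4.

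The cost is one on-treatment flag and an extra set of tables. The downside is that late non-serious events leave the main table, though they remain visible in the post-treatment one.

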### **2.6.1.1 Adverse events of special interest / grouping of AEs**

Adverse of special interest were

- New onset of diabetes mellitus,
- de novo HCC malignancies,
- HCV- and HCV-related fibrosis
- Proteinuria
- CMV viral infections

For the subgroup of patients with HbA1c baseline range of 5.7 to 6.4%, the onset of diabetes will be calculated additional.

### **2.6.2 Deaths**

Adverse events leading to death will be listed by treatment group.

### **2.6.3 Laboratory data**

Abnormalities according notable criteria (see Appendix 2 of the study protocol) were identified. The proportions of patients with clinically notable abnormalities according to the notable criteria were summarized. Descriptive statistics of absolute values as well as change from baseline of all laboratory variables were presented by visit and treatment group. A by-

patient listing of all clinically notable abnormal laboratory data was generated. Only assessments obtained up to 28 days after the discontinuation of study medication will be considered “on-treatment” and analyzed with relationship to immunosuppressive therapy.

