### **Changes to the protocol**

The major changes that are made to the protocol are as follows:

- Measurement of the Tacrolimus C-0h levels can now be performed as per local practice (section 4 and 6.3)
- Inclusion criteria – randomization 2 was rephrased for a clearer understanding (section 5.1).
- Inclusion criteria – randomization 3: AST and ALT levels were raised to  $\leq 5$  times ULN, evaluation of gamma GT was deleted due to the fact that it does not reflect a prognostically important marker (section 5.1).
- For a better understanding, exclusion criteria – randomization 2 was separated in 4 independent criteria. Platelet, neutrophil and white blood cell count was reduced to 50,000/mm^3, 1,000/mm^3 and 2,000/mm^3 respectively (section 5.1).
- Former inclusion criteria – randomization 2 (now 6): Calculation mistake of concentration of hypertriglyceridemia was corrected (section 5.1).
- Graft loss was added as reason for premature patient withdrawal (section 5.2).
- Dispensing of study drug and instruction for use of study drug are described in more detail to avoid misuse (section 6.6.1, 6.6.2).
- According to the adaptation of in- and exclusion criteria, the permission of study drug adjustment and interruption in case of inability of tolerance of the protocol-specific dosing scheme is described in more detail (section 6.6.3 and appendix 5)
- PCP prophylaxis and treatment of oral candida will be performed according to local practice (section 6.6.5)
- It was added, that pregnancy outcomes must be collected for the female partners of any males who took study drug in this study (section 8.2)

Changes to specific sections of the protocol are shown in the track changes version of the protocol using ~~strike through red font~~ for deletions and red underlined for insertions.

A copy of this CRAD001HDE13 Protocol Amendment will be sent to the EC for review. The changes described in this amendment require IRB/EC approval prior to implementation.

In addition, a revised informed consent that takes into account the changes to the protocol described herein will be submitted to the IRB/EC for approval.

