#### **Inclusion Criteria - Randomization**

1. eGFR (MDRD4 formula) > 30 mL/min/1.73m^2 at time of randomization.
2. Absence of thrombosis via Doppler ultrasound of the major hepatic arteries, major hepatic veins, portal vein and inferior vena cava at time of randomization and prior to any initiation of treatment with everolimus.
3. Allograft is functioning at an acceptable level by the time of randomization as defined by total bilirubin levels  $\leq$ 3 times ULN and AlkP, AST, ALT levels  $\leq$  5 times ULN.

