#### **Exclusion Criteria - Randomization**

1. Patients who are not able to take oral medication at time of randomization.
2. Patients with platelet count <50,000/mm^3)
3. Patients with an absolute neutrophil count of <1,000/mm^3
4. Patients with a white blood cell count of <2,000/mm^3)
5. Patients with hemoglobin < 6.0 g/dL.(transfusion of erythrocytes concentrate during or after transplantation are allowed according to investigator discretion.)
6. Patients with uncontrolled hypercholesterolemia (>350mg/dL; >9mmol/L) or hypertriglyceridemia (>750 mg/dL, >8.5 mmol/L).
7. Patients with a protein/creatinine ratio indicating daily urinary protein excretion >1 g/24h at time of randomization.
8. Patients with clinically significant or uncontrolled systemic infection requiring active use of IV antibiotics at the time of randomization.

9. Patients who have received an investigational drug within 30 days prior to randomization.

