## **Laboratory data**

Abnormalities according notable criteria (see [Appendix 2](#)) will be identified. The proportions of patients with clinically notable abnormalities according to the notable criteria will be summarized. Shifts from baseline value to worst post-baseline value based on the normal ranges will be presented graphically ([Amit et al., 2008](#)). The worst observation is defined as the highest or lowest measure during the different observations periods whereby high or low are chosen according to the direction of abnormality. Descriptive statistics of absolute values as well as change from baseline of all laboratory variables will be presented by visit and treatment group. A by-patient listing of all clinically notable abnormal laboratory data will be generated. Only assessments obtained up to 28 days after the discontinuation of study medication will be considered “on-treatment” and analyzed with relationship to immunosuppressive therapy.

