## 13.2 Appendix 2: Clinically notable laboratory values and vital signs

Laboratory variable	Standard units	SI units
Liver function and related variables		
SGOT (AST)	$\geq 3 \times$ ULN	$\geq 3 \times$ ULN
SGPT (ALT)	$\geq 3 \times$ ULN	$\geq 3 \times$ ULN
Bilirubin	$\geq 3 \times$ ULN	$\geq 3 \times$ ULN
Renal function, metabolic and electrolyte variables		
Urea	None	None
Creatinine	Day 8 or after: $>30\%$ above value from preceding visit or Day 8 to Wk 4: $\geq 4$ mg/dL, After Wk 4: $\geq 3$ mg/dL	Day 8 or after: $>30\%$ above value from preceding visit or Day 8 to Wk 4: $\geq 354$ $\mu\text{mol/L}$ , After Wk 4: $\geq 265$ $\mu\text{mol/L}$
Uric acid	M $\geq 12$ mg/dL F $\geq 9$ mg/dL	M $\geq 714$ $\mu\text{mol/L}$ F $\geq 535$ $\mu\text{mol/L}$
Glucose	<45 mg/dL $>250$ mg/dL	<2.5 mmol/L $>13.9$ mmol/L
Cholesterol	$\geq 350$ mg/dL	$\geq 9.1$ mmol/L
Triglycerides	$\geq 750$ mg/dL	$\geq 8.5$ mmol/L
CPK (MB)	None	None
Potassium	$\leq 3.0$ mEq/L $\geq 6.0$ mEq/L	$\leq 3$ mmol/L $\geq 6$ mmol/L
Calcium	$\leq 6$ mg/dL $\geq 13$ mg/dL	$\leq 1.5$ mmol/L $\geq 3.2$ mmol/L
Hematology variables		
Hemoglobin	<7 g/dL	<4.39 mmol/L
Platelets (thrombocytes)	$<50$ k/mm  $\geq 700$ k/mm 	$<50 \times 10^9$ /L $\geq 700 \times 10^9$ /L
Leukocytes (WBCs)	$\leq 2.0$ k/mm  $\geq 16$ k/mm 	$\leq 2.0 \times 10^9$ /L $\geq 16 \times 10^9$ /L
Hematology variables: differential		
Granulocytes (poly, neutrophils)	$\leq 1,000$ /mm 	$\leq 1 \times 10^9$ /L
Eosinophils	$\geq 12\%$	$\geq 12\%$
Lymphocytes	$\leq 1,000$ /mm 	$\leq 1 \times 10^9$ /L

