**Amendment 4 (19-NOV-2014):** 186 patients had been randomized to the study:

The protocol had been refined to clarify the mandatory usage of corticosteroids in this study. Additionally, Inclusion Criterion 3/Exclusion Criterion 11 had been adjusted to include total abstinence as acceptable contraception method.

**Amendment 5 (19-AUG-2015):** 259 patients had been randomized to the study:

The purpose of this amendment was to adapt one exclusion criteria (Excl.Crit.N°5) to better align with given clinical praxis and patients' condition post liver transplantation. Therefore Exclusion Criterion 5 (at randomization) had been adjusted to allow inclusion of patients with hemoglobin < 6.0 g/dL (transfusion of erythrocytes concentrate during or after transplantation are allowed according to investigator discretion).

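### For AST, ALT and haemoglobin a patient can be eligible at randomisation and already clinically notable, and SAP 2.6.3 sets no baseline condition on the notable count; the protocol's shift display is also dropped without being declared

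*SAP*

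**What the plan says.** SAP 2.6 rests the safety assessment mainly on adverse events and on laboratory values outside set ranges. For the latter, SAP 2.6.3 states: "The proportions of patients with clinically notable abnormalities according to the notable criteria were summarized". The criteria are those of Protocol Appendix 2 ("Clinically notable laboratory values and vital signs"). The only time limit given is an upper one, 28 days after study medication stops. The section also keeps absolute values and change from baseline by visit and arm, and a by-patient listing of notable values.

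Entry at randomisation is governed by Protocol 5.1. The graft-function criterion begins "Allograft is functioning at an acceptable level by the time of randomization as defined by total bilirubin levels" (limit 3 x ULN) and continues with "AlkP, AST, ALT levels $\leq$ 5 times ULN". The haemoglobin exclusion is "Patients with hemoglobin < 6.0 g/dL".

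Protocol 10.5.2 (Laboratory data) plans the same notable proportion, also without a baseline condition, and adds a display: "Shifts from baseline value to worst post-baseline value based on the normal ranges will be presented graphically". SAP 2.6.3 does not contain that display. The changes in statistical methods listed in SAP Section 4 do not mention its removal.

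**The concern.** Patients are randomised 7 to 21 days after liver transplantation, when raised transaminases or anaemia may still reflect the operation. The first post-baseline laboratory visit is Day 8, with a window of 3 days either way (Protocol Section 7), while the everolimus target level is due only within 14 days of randomisation (Protocol 6.6.2). A patient who enters with ALT at 4 x ULN and is still there at Day 8 meets the notable criterion although nothing new has happened.

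If such patients are counted, the table mixes what they brought into the trial with what arose during it. The absolute rates are then too high as a description of on-treatment abnormality, and a true difference between arms looks smaller in relative terms. Haemoglobin matters here because a fall in it is one of the named reasons for everolimus dose adjustment (Protocol 6.6.3 and Appendix 5).

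**Working it through.** **Step 1. Entry limit against notable limit** (Protocol 5.1 against Appendix 2, standard units), for analytes that carry a randomisation limit.

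| Analyte | Admitted | Notable | Overlap |
|---|---|---|---|
| AST, ALT | up to and including 5 x ULN | 3 x ULN or more | 3 to 5 x ULN |
| Haemoglobin | 6.0 g/dL or more | below 7 g/dL | 6.0 to below 7 g/dL |
| Bilirubin | up to and including 3 x ULN | 3 x ULN or more | exactly 3 x ULN |
| Neutrophils | 1,000/mm³ or more | 1,000/mm³ or less | exactly 1,000 |
| White cells (low) | 2,000/mm³ or more | 2,000/mm³ or less | exactly 2,000 |
| Cholesterol | up to 350 mg/dL | 350 mg/dL or more | exactly 350 |
| Triglycerides | up to 750 mg/dL | 750 mg/dL or more | exactly 750 |
| Platelets (low) | 50,000/mm³ or more | below 50,000/mm³ | none |

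Creatinine is limited at entry through eGFR > 30. Inverting MDRD-4 at 30 for a man aged 18 gives (186.3 x 18^-0.203 / 30)^(1/1.154) = 2.93 mg/dL, or 3.45 mg/dL with the factor R = 1.21. Both lie below the 4 mg/dL rule for Day 8 to Week 4. The creatinine rule also has its own Day 8 start and an alternative based on the preceding visit. AST, ALT and haemoglobin have no such condition. Analytes with no entry limit, such as glucose or lymphocytes, are not tested by this comparison.

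**Step 2. How many patients the limits reach.** Amendment 2, which changed the transaminase limit ("AST and ALT levels were raised to" 5 x ULN), came when 15 patients had been randomised, so about 330 - 15 = 315 of the planned 330 entered under it. Amendment 5, on haemoglobin, came after 259 randomisations (SAP Section 4), leaving 330 - 259 = 71 planned patients (71/330 = 22%). The earlier haemoglobin limit is not given. If it was 7 g/dL or higher, the haemoglobin overlap concerns at most those 71, and among them only those inside a 1 g/dL band.

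**Step 3. Size of the dilution.** The plan gives no figure to reproduce, so this is an illustration. Let p0 be the share already notable at baseline, equal in both arms and all counted, and r the new-onset rate among the others.

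Tabulated rate = p0 + (1 - p0) x r. Risk difference = (1 - p0) x (r1 - r2).

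Take r = 10% and 5% (ratio 2.00, difference 5.0 points). For p0 = 10%: 0.10 + 0.90 x 0.10 = 19.0%; 0.10 + 0.90 x 0.05 = 14.5%; ratio 1.31.

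| p0 (assumed) | Rates | Ratio | Difference (points) |
|---|---|---|---|
| 2% | 11.8% v 6.9% | 1.71 | 4.9 |
| 5% | 14.5% v 9.75% | 1.49 | 4.75 |
| 10% | 19.0% v 14.5% | 1.31 | 4.5 |
| 20% | 28.0% v 24.0% | 1.17 | 4.0 |

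Restricting the count to patients not notable at Visit 2 returns 10% v 5% in every row.

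**Step 4. The dropped display.** The protocol's shifts were to be drawn against normal ranges, not notable limits. They would have shown baseline status beside the worst later value, but would not have altered the notable proportion. The undeclared omission and the missing baseline condition are two separate points.

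**The case against.** The strongest reply is that this is a descriptive safety table with no test attached and no bearing on the primary or key secondary analysis, and that other outputs already take baseline into account. SAP 2.6.3 keeps change from baseline by visit and arm, and Protocol 7.6.1 defines adverse events as new or worsening conditions. That stands, and it limits the weight of the point. It does not remove it: neither a summary of change nor a listing gives the per-arm rate of newly notable patients.

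The counting rule is also read from silence. The SAP does not say whether the Visit 2 sample counts, and the note to file shows that table shells sit in a separate document (RAP Module 6) that is not available here. A baseline rule may exist there; the SAP text does not supply one.

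The missing condition is not a change made by the SAP, since Protocol 10.5.2 lacks it too. Only the shift display was dropped.

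Three stronger readings are tempting and are not supported:

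- A reader might infer that the notable limits overlap the entry criteria generally. Among analytes with an entry limit, only AST, ALT and haemoglobin overlap over a range.
- A reader might infer that a drug effect is hidden, or that one arm is favoured. Randomisation balances prevalent abnormalities in expectation, so the effect is dilution. Even at an assumed 20% baseline share, 4.0 of the 5.0 points of risk difference remain.
- A reader might infer that keeping the shift display would have corrected the proportion. It would not (Step 4).

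**Conclusion.** The point holds in a limited form. For AST and ALT between 3 and 5 x ULN and haemoglobin from 6.0 to below 7 g/dL, eligibility and notability coincide, and nothing in SAP 2.6.3 stops carried-over values from entering the on-study count. The consequence is inflated absolute rates in both arms and a ratio drawn toward 1.

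The size cannot be fixed from the documents. Under the illustration, a true ratio of 2.0 reads as anything from 1.71 (2% notable at baseline) to 1.17 (20%). This assumes equal baseline shares, new-onset rates of 10% and 5%, and that every baseline-notable patient is counted; if some have resolved and the Visit 2 sample is not counted, the dilution is smaller. The transaminase part reaches nearly all planned patients' entry rules. The haemoglobin part may concern few.

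The undeclared loss of the protocol's shift display stands on its own, whatever the size of the dilution. Together these justify an inexpensive improvement to the safety tables. They do not put the trial's main conclusions in doubt.

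**What to change.** In SAP 2.6.3:

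1. State that the notable proportion uses post-baseline values only.
2. Beside the existing all-patient proportion, report newly notable abnormalities, with patients not notable at Visit 2 as the denominator, at least for AST, ALT and haemoglobin.
3. Restore the baseline-to-worst-value display, using actual values or graded categories so that worsening in patients already notable at entry can be seen. If it is not restored, list its removal, with the reason, in SAP Section 4.

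No entry criterion or notable threshold needs to change for this. Haematology and biochemistry are already scheduled at Visit 2, so the cost is SAP wording and a few extra tables. The one drawback is that a new-onset count alone leaves out patients who enter notable and then get worse. Keeping the all-patient proportion and adding the item 3 display covers that.
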